3. KSS-FUNCTION SCORE			
Walking aids  None  Unlimited  Cane  > 10 blocks / > 1000m, > 3280 feet  Two canes / one crutch  5-10 blocks / 500m - 1000m, 1640-3280 feet  Crutches or walker, cannot walk / wheelchair  < 5 blocks / < 500m, < 1640 feet  Housebound		Walking  Normal up & down  Normal up; down with rail  Up & down with rail  Up with rail; unable down  Unable	
 Function motion score not done			
Investigator Name (Print)			INITIAL/DATE
Investigator Signature			Monitored: /
Date			Receipt: /
			Entry: /
			Verification: /

Stryker® Simplex HV Retrospective Study				
Page 1 of 2	OKS	Patient ID	8 0	Study#, Center#, Subject#, Side (UR)
GENERAL INFORMATION				
Patient code (Use AA, BB,...AB)		Date of examination		
Pre-op visit		Follow-up at	 12-24 months (+2 months) post study surgery	 5 years (\pm 3 months) post study surgery, specify
				 years  months
OKS SCORE				
1. How would you describe the pain you usually have in your knee?				
 None	 Very mild	 Mild	 Moderate	 Severe
2. Have you had any trouble washing and drying yourself (all over) because of your knee?				
 No trouble at all	 Very little trouble	 Moderate trouble	 Extreme difficulty	 Impossible to do
3. Have you had any trouble getting in and out of the car or using public transport because of your knee? (With or without a stick)				
 No trouble at all	 Very little trouble	 Moderate trouble	 Extreme difficulty	 Impossible to do
4. For how long are you able to walk before the pain in your knee becomes severe? (With or without a stick)				
 No pain > 60 min	 16 - 60 minutes	 5 - 15 minutes	 Around the house only	 Not at all - severe on walking
5. After a meal (sat at a table), how painful has it been for you to stand up from a chair because of your knee?				
 Not at all painful	 Slightly painful	 Moderately pain	 Very painful	 Unbearable
6. Have you been limping when walking, because of your knee?				
 Rarely / Never	 Sometimes or just at first	 Often, not just at first	 Most of the time	 All of the time
7. Could you kneel down and get up again afterwards?				
 Yes, easily	 With little difficulty	 With moderate difficulty	 With extreme difficulty	 No, impossible

Please continue on page 2 of 2

Stryker® Simplex HV Retrospective Study																																																											
Page 2 of 2	OKS	Patient ID	8 0	Study#	Center#	Subject#	Side (L/R)																																																				
GENERAL INFORMATION																																																											
Patient code (Use AA, BB,...AB)	Date of examination	
 
 D D	M M M	Y Y Y Y	
 
 years	months		
 
								D D	M M M	Y Y Y Y	years	months																																													
D D	M M M	Y Y Y Y																																																									
years	months																																																										
Pre-op visit 	Follow-up at  12-24 months (+2 months) post study surgery																																																										
	 5 years (\pm 3 months) post study surgery, specify																																																										
OKS SCORE																																																											

8. Are you troubled by pain in your knee at night in bed?
 
 
 	
 
 Not at all	Only one or two nights	Some nights	Most nights	Every night	
 
 
9. How much has pain from your knee interfered with your usual work? (including housework)
 
 
 	
 
 Not at all	A little bit	Moderately	Greatly	Totally	
 
 
10. Have you felt that your knee might suddenly give away or let you down?
 
 
 	
 
 Rarely / Never	Sometimes or just at first	Often, not at first	Most of the time	All the time	
 
 
11. Could you do household shopping on your own?
 
 
 	
 
 Yes, easily	With little difficulty	With moderate difficulty	With extreme difficulty	No, impossible	
 
 
12. Could you walk down a flight of stairs?
 
 
 	
 
 Yes, easily	With little difficulty	With moderate difficulty	With extreme difficulty	No, impossible	
 
											Not at all	Only one or two nights	Some nights	Most nights	Every night		Not at all	A little bit	Moderately	Greatly	Totally		Rarely / Never	Sometimes or just at first	Often, not at first	Most of the time	All the time		Yes, easily	With little difficulty	With moderate difficulty	With extreme difficulty	No, impossible		Yes, easily	With little difficulty	With moderate difficulty	With extreme difficulty	No, impossible																				
																																																											
Not at all	Only one or two nights	Some nights	Most nights	Every night																																																							
																																																											
Not at all	A little bit	Moderately	Greatly	Totally																																																							
																																																											
Rarely / Never	Sometimes or just at first	Often, not at first	Most of the time	All the time																																																							
																																																											
Yes, easily	With little difficulty	With moderate difficulty	With extreme difficulty	No, impossible																																																							
																																																											
Yes, easily	With little difficulty	With moderate difficulty	With extreme difficulty	No, impossible																																																							
Investigator Name (Print)					For Stryker Use Only		INITIAL/DATE:																																																				
Investigator Signature					Stamp Date Received:		Monitored: _____ / _____																																																				
Date	
 
 D D	M M M	Y Y Y Y	
 
 years	months		
 
				D D	M M M	Y Y Y Y	years	months							Receipt: _____ / _____																																											
D D	M M M	Y Y Y Y																																																									
years	months																																																										
							Entry: _____ / _____																																																				
							Verification: _____ / _____																																																				

Stryker® Simplex HV Retrospective Study			
Page 1 of 2	ADVERSE EVENT REPORT	Patient ID	8 0 Center# Subject# Side (L/R)
GENERAL INFORMATION			
Patient code (Use AA, BB,..AB)		AE start date	
Occurrence:	 Intra-op  post-op		
Adverse Event Information (use one form per complication/event)			
Event Description			
 Aseptic loosening of study device	 Other event	 specify	
Date of study surgery		Date event resolved	
	D D M M M Y Y Y Y	D D M M M Y Y Y Y	 not resolved
Adverse Event Group		Type of Event <small>please follow protocol chapter 6</small>	
 Elective Surgery	 AE	 SADE	
 Operative Site Event	 ADE	 Device Deficiency	
 Systemic event	 SAE		
<small>ISO14155: Planned hospitalization for a preexisting condition, without serious deterioration in health, is not considered a complication/serious adverse event</small>			
Seriousness			
 Not serious			
 Led to death			
 Led to serious deterioration in the health of the subject, resulting in:			
 A life-threatening illness or injury  A permanent impairment of a body structure or function  In-patient or prolonged hospitalization  Medical or surgical intervention to prevent life-threatening illness or injury or permanent impairment to a body structure or a body function  Led to foetal distress, foetal death or a congenital abnormality or birth defect			
Device Relation		Surgery Relation	Key
 yes ^{1,2}	 yes ¹	¹ Complete device information on page 2	
 no	 no	² Verify if complication was reported to Stryker	
 uncertain ^{1,2}	 uncertain ¹		
Treatment			
 Revision/Removal due to aseptic loosening of study device	Revision date 		
 Other operative treatment of operative side, specify			
 Other treatment, specify			

Please continue page 2 of 2

Stryker® Simplex HV Retrospective Study					
Page 2 of 2	ADVERSE EVENT REPORT	Patient ID	8 0	Study#	Center#
				Subject#	Side (L/R)
GENERAL INFORMATION					
Patient code (Use AA, BB,...AB)		AE start date			
Occurrence:	 intra-op  post-op		D D	M M M	Y Y Y Y
Adverse Event (MedDRA category)					
Device Information (if certain or uncertain device or surgery relation)					
Component	Ref./Catalogue number	Lot/Case Code			
Simplex HV					
Simplex HV, Antibiotic					
Femur component					
Tibial Component					
Insert					
Patella (if applicable)					
Adverse Event (MedDRA category)					
 Blood and Lymphatic System Disorders  Cardiac Disorders  Congenital, Familial and Genetic Disorders  Ear and Labyrinth Disorders  Endocrine Disorders  Eye Disorders  Gastrointestinal Disorders  General Disorders and Administration Site Conditions  Hepatobiliary Disorders  Immune System Disorders  Infections and Infestations  Injury, Poisoning and Procedural Complications  Investigations  Metabolism and Nutrition Disorders  Musculoskeletal and Connective Tissue Disorders  Neoplasms Benign and Malignant (Incl Cysts and Polyps)  Nervous System Disorders  Pregnancy, Puerperium and Perinatal Conditions  Psychiatric Disorders  Renal and Urinary Disorders  Reproductive System and Breast Disorders  Respiratory, Thoracic and Mediastinal Disorders  Skin and subcutaneous Tissue Disorders  Social Circumstances  Surgical and Medical Procedures  Vascular Disorders					
Investigator Name (Print)			For Stryker Use Only		INITIAL/DATE:
Investigator Signature			Stamp Date Received:		Monitored: /
Date					Receipt: /
					Entry: /
					Verification: /

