1.1 Background

The American Joint Replacement Registry (AJRR) shows an annual increase from approximately 20,000 to almost 130,000 in primary TKAs from 2012 to 2017. In the same time the use of High Viscosity Cement (HVC) in primary knee arthroplasty increased steadily from 46% to 61%¹.

Most of commercially available acrylic bone cements are based upon polymethylmethacrylate (PMMA) and methylmethacrylate (MMA) systems and consist of powdered and liquid components². The polymerization of bone cement occurs through a progression of 4 phases: mixing phase, waiting phase, working phase, and hardening phase. HVC has some advantages over low-viscosity cement (LVC) including shorter mixing and waiting phases, whereas the working and hardening phases are longer. Operational efficiencies are receiving greater interest by surgeons and hospital administrations because high viscosity (HV) bone cements provide a shorter dough time than medium viscosity cements, which may result in surgical efficiencies by

allowing surgeons to handle and apply the cement to implant components and bone earlier while having more time to work with the cement during implantation of the components.^{1,2,3}.

The most common reason for failure of TKA is infection followed by implant loosening, polyethylene wear, and instability⁴. With the use of HVC, the literature describes a focus on aseptic loosening of the tibial component probably resulting from debonding of the cement-tray interface^{3,4}. Considering the exact cause may be unknown, some authors suggest associations of this type of failure to the use of high-viscosity cement^{5,6}. In contrast, a retrospective review of 1851 cases of primary TKA (obese patients with BMI >35) using HVC mixed with Gentamicin showed one revision due to aseptic loosening³.

This study is a retrospective investigation of subjects who have received primary Triathlon Total Knee Arthroplasty inserted with Simplex High Viscosity (HV) Cement to evaluate the success rate defined as absence of revision for aseptic loosening of components at two years postoperative.

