9.2 Safety

9.2.1 Safety Parameters

Safety parameters include all protocol-defined adverse events as well as revision and/or removal rates. For details regarding protocol-defined adverse events, see Section 6.1.

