6. POST-OP SERIOUS ADVERSE EVENT/DEVICE DEFICIENCY										
 No	 Yes, due to aseptic loosening*			 Yes, due to other reason*						
*If yes, please specify in Adverse Event Form										
Investigator Name (Print)					For Stryker Use Only					
Investigator Signature					Stamp Date Received:					
Date										
	D	D	M	M	M	Y	Y	Y	Y	
INITIAL/DATE										
					Monitored: _____ / _____					
					Receipt: _____ / _____					
					Entry: _____ / _____					
					Verification: _____ / _____					

Stryker® Simplex HV Retrospective Study			
Page 1 of 1	Knee Society Score	Patient ID 8 0	
		Study#	Center#
		Subject#	Side (L/R)
GENERAL INFORMATION			
Patient code (Use AA, BB,...AB)		Date of examination 	
Pre-op visit 	Follow-up at  12-24 months (+2 months) post study surgery  5 years (± 3 months) post study surgery, specify 		

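### Revisions for causes other than aseptic loosening are captured only as free text without an operation date, although 9.2.1 and 9.4.1 call for revision rates and an all-cause survivorship curve

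*Combined protocol and SAP*

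**What the plan says.** The Treatment block of the Adverse Event Report form (Appendix B) has three options:

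- "Revision/Removal due to aseptic loosening of study device", with the field "Revision date" on the same row;
- "Other operative treatment of operative side, specify", a free-text line with no date;
- other treatment, also free text.

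Higher up, the form codes the event either as "Aseptic loosening of study device" or as another event to be specified. It also records the start date of the event, the date of the study surgery and the "Date event resolved", with an alternative for events that have not resolved.

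On the Follow-up form, item 5 asks for surgery dates for the other knee and both hips. Item 6 separates aseptic loosening from "Yes, due to other reason" and refers back to the adverse event form.

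Section 9.2.1 states: "Safety parameters include all protocol-defined adverse events as well as revision and/or removal rates". Section 9.4.1 plans an aseptic-loosening Kaplan-Meier curve for the non-medicated cement. For the gentamicin cement it plans a curve described as all-cause at the start of the sentence and as for aseptic loosening at the end.

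**The concern.** Two planned outputs need more than the aseptic-loosening revisions. The safety parameter in 9.2.1 is not limited by cause, and 9.4.1, on one of its two readings, needs the time of every revision. The form gives structure to one cause only. A removal for infection, instability or wear shares a free-text line with washouts, manipulations and arthroscopies, and the date of the operation is not requested.

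The aseptic-loosening curves are affected too. A knee whose index components have been removed for another reason can no longer have them revised for loosening, so it should leave the risk set on the day of removal. The form does not ask for that day, and the plan states no censoring rule for this case.

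The protocol's background gives a reason not to treat other causes as negligible: "The most common reason for failure of TKA is infection followed by implant loosening, polyethylene wear, and instability".

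**Working it through.** The plan gives no figure to reproduce. The check sets the data each output needs against the fields on the forms, for a revision not due to aseptic loosening.

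1. **Is it reported at all?** Yes. Section 6.1 requires every adverse event at the operative site to be reported, serious or not.
2. **Is there a coded revision field?** No. The only coded option names aseptic loosening.
3. **Can it be found?** Yes, by reading the free text under other operative treatment and under other event. Page 2 adds a MedDRA category, but does not say whether components were removed. It asks for component catalogue and lot numbers only when a device or surgery relation is certain or uncertain, and does not ask which components were revised.
4. **Is the operation dated?** No. The start date gives onset and the resolution date gives the end, which may be left as unresolved. Take an infection with onset at month 23, treated by washout and then by component removal at month 26. The start date puts it before the 24-month endpoint; the removal came after it.
5. **Does the Follow-up form fill the gap?** No. Item 5 dates replacements of the other three joints but not a reoperation on the study knee, and item 6 has no revision field.

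What follows for each output:

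- **Revision/removal rate (9.2.1):** obtainable, after someone codes the free text. A crude rate needs no date. Section 9.2.2 tabulates adverse events only and does not say how this rate will be produced.
- **All-cause Kaplan-Meier curve (9.4.1, if that reading is meant):** the exact event time is not captured; adverse event dates are proxies.
- **Aseptic-loosening curves (9.4.1):** the exact censoring time is not captured.

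Illustration of size. The documents give no rate of other-cause revision, so assume 1 to 3 per 100 knees by 24 months, with 100 knees per arm as planned:

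- Part of the all-cause rate that rests on free text: 1/100 = 1.0% to 3/100 = 3.0%.
- Effect on the aseptic-loosening estimate: assume further one loosening revision, occurring after all 3 other-cause removals. Censoring those 3 gives 1 − 1/97 = 98.97%. Leaving them at risk gives 1 − 1/100 = 99.00%. The difference is about 0.03 percentage points.

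**The case against.** A reader might infer that other-cause revisions can be neither identified nor dated. The documents do not support that. Such a revision has a place on the form, can be recognised from its free text, and carries start and resolution dates. Sections 8.3 and 10.1 have monitors compare the forms with source records, and section 8.4 allows unclear entries to be queried. With a handful of events per arm, reading the lines by hand would give a count.

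A reader might also infer that these knees will stay at risk to 24 months and be counted as successes of the original fixation. No section states such a rule. Approximate censoring from the adverse event dates is possible. Moreover, a knee revised for infection is not a failure under 9.1.1 because of how the endpoint is defined, whatever the form asks.

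The background ranking concerns knee replacement failures in general. It does not describe the first 24 months or this cohort, which excludes active or suspected latent infection (criterion E), so it cannot show that most revisions here would fall on the free-text line.

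All of this stands. It does not supply the operation date or a coded field. Queries can recover both, but only as a repair after the paper forms have been completed.

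**Conclusion.** The point holds as a limited data-capture defect. Revisions for causes other than aseptic loosening are uncoded, mixed with non-revision operations, and lack an operation date. The rates in 9.2.1 need manual coding, the all-cause curve in 9.4.1 has no exact event date, and the aseptic-loosening curves have no exact censoring date. On the assumed 1 to 3 events per 100 knees, the whole non-loosening part of the all-cause rate is exposed, while the aseptic-loosening estimate hardly moves.

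Three conditions apply:

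- The need for an event date in the gentamicin curve depends on how the contradictory sentence in 9.4.1 is reconciled.
- The form was read from extracted text. The revision-date field appears on the aseptic-loosening row, but the printed layout could not be seen.
- Exclusion criterion A in section 5.1 bars patients who have had revision surgery. If it is applied to revisions after the index operation, those knees never reach the adverse event form and a better field recovers nothing.

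**What to change.** - **Adverse Event Report form, Treatment:** replace the revision option with revision or removal of any study-knee component, with operation date and cause (aseptic loosening, or other to be specified). Keep reoperations without component revision as a separate option. A list of components revised and a longer list of causes are optional.
- **Section 9.2.2:** report the all-cause revision/removal rate by cement type from this field.
- **Section 9.4.1:** reconcile the gentamicin sentence so that it names either all-cause or aseptic-loosening revision, and state that the aseptic-loosening curves are censored at the date of any other-cause revision.
- **Section 5.1, criterion A:** make clear that it does not remove knees revised after the index surgery; otherwise the changes above have no effect.

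The cost is one revised form item, a few lines of text and slightly more abstraction from hospital records that the sites already review. The reported all-cause rate may be less favourable. Making the change before the forms are completed avoids going back to the sites with queries.

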7.1 Definition of Aseptic Loosening

X-rays will be collected at least at two years after surgery for independent analysis of radiolucency occurrence at implant-cement interface by an independent reviewer

[figure not shown]
- Radiolucency at implant-cement interface
 - Tibia A/P
 - Tibia lateral
 - Femur PS lateral or Femur CR lateral

Radiolucencies at the implant-cement interface more than 2 mm in all zones of a component is defined as aseptic loosening.

[figure not shown]
Zones Tibia A/P⁷

Zones Tibia Lateral⁷

Zones Femur PS Lateral⁷

Zones Femur CR Lateral⁷

[figure not shown]

Figure 2 Component zones

8 Data Management

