9.1 Study Objectives

9.1.1 Objective Analysis

To evaluate the success rate of cemented Triathlon Total Knee components implanted using Simplex high viscosity bone cement (Simplex HV). Success is defined as absence of revision of cemented Triathlon Total Knee components implanted with Simplex HV for aseptic loosening at two years postoperative. 95% confidence interval of the success rate will be presented as well.

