9.4 Statistical Methodology

9.4.1 Data Summary

Descriptive statistics will be computed for all baseline conditions and demographic parameters. That is, for continuous data, the N, mean, median, standard deviation, minimum and maximum will be computed. For categorical data, the frequency will be computed. The data will be presented by appropriate subgroups (e.g., center, gender).

A Kaplan-Meier survivorship curve will be displayed for revision and/or removal of the Triathlon total knee arthroplasty cemented with Simplex HV for aseptic loosening.

A Kaplan-Meier survivorship curve will be displayed for all-cause revision and/or removal of the Triathlon total knee arthroplasty cemented with Simplex HV with Gentamicin for aseptic loosening.

Two year Kaplan-Meier success rate with 95% CI will be presented.

For all additional data collected that are not required for direct support of a study objective, data will be summarized according to follow-up. For parameters represented by continuous variables (e.g., ROM), the summaries will consist of the N, mean, median, standard deviation, minimum, and maximum values.

Documentation of statistical analyses utilizing SAS® software version 9.3 or higher will be maintained.

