9.4.2 Sample Size Justification

No sample size calculation because a number of 100 cases per study arm was pre-defined by the regulatory body.

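### The primary rate counts only revisions the site attributes to aseptic loosening, and no planned analysis shows how far it depends on that attribution

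*Combined protocol and SAP*

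**What the plan says.** The endpoint is cause-specific. Section 9.1.1 states: "Success is defined as absence of revision of cemented Triathlon Total Knee components implanted with Simplex HV for aseptic loosening at two years postoperative". It adds that the "95% confidence interval of the success rate will be presented as well", and 9.4.1 says "Two year Kaplan-Meier success rate with 95% CI will be presented". On size, 9.4.2 gives "No sample size calculation because a number of 100 cases per study arm was pre-defined by the regulatory body". There is no hypothesis, margin or performance goal.

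The site enters the cause in three fields on two forms in Appendix B:

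- **Follow-up form, item 6:** the choice is none, due to aseptic loosening, or due to another reason.
- **Adverse Event form, event description:** aseptic loosening or another event.
- **Adverse Event form, treatment:** "Revision/Removal due to aseptic loosening of study device", with a revision date. As the form's text reads, surgery on the operated side for any other reason goes to a free-text line with no revision date.

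Two other analyses touch revision. Section 9.2.1 names revision and removal rates as safety parameters, with no cause given. Section 9.4.1 plans one curve for the non-medicated cement (aseptic loosening) and one for the gentamicin cement. The second is introduced as all-cause, but the same sentence ends by restricting it to aseptic loosening.

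**The concern.** A knee revised for loosening but written up as pain or instability is not a primary failure. With 100 knees per cement and few events, a single attribution shows in both the estimate and its interval, and these two figures are the whole primary result. A reader shown only the cause-specific rate cannot tell whether a figure near 100% reflects few revisions of any kind, or several that were put down to other reasons.

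The all-cause rate would answer this, but as the plan stands it is not clearly produced for either cement. The non-medicated group has no all-cause curve, the gentamicin curve is ambiguous, and the 9.2.1 rates have no time point, interval or link to the primary rate. The date needed to place an other-cause revision before or after 24 months is not clearly collected.

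**Working it through.** The plan gives no event rate or precision figure to reproduce, so the check asks how far one reattributed revision moves the planned result.

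**Inputs.** n = 100 per cement (9.4.2). The interval is 95% (9.1.1), taken as two-sided because the plan states neither sidedness nor method. All knees have at least 24 months of follow-up (5.1, inclusion C), so without earlier censoring the two-year Kaplan-Meier rate equals the simple proportion. The number of failures k is assumed.

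**Formula.** The rate is (n − k)/n. The exact (Clopper-Pearson) lower limit is the 2.5% quantile of Beta(n − k, k + 1), and the upper limit is the 97.5% quantile of Beta(n − k + 1, k), or 100% when k = 0. For k = 0 the lower limit is 0.025^(1/100) = 96.38%.

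| Failures k of 100 | Rate | Exact 95% interval | Fall in lower limit from k − 1 |
|---|---|---|---|
| 0 | 100% | 96.38 to 100 | – |
| 1 | 99% | 94.55 to 99.97 | 1.83 |
| 2 | 98% | 92.96 to 99.76 | 1.59 |
| 3 | 97% | 91.48 to 99.38 | 1.48 |
| 4 | 96% | 90.07 to 98.90 | 1.41 |

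Each reattribution therefore costs 1.0 point in the rate and 1.4 to 1.8 points in the lower limit. If the two cements were pooled (n = 200), each would cost 0.5 point, and the lower limit would go 98.17, 97.25, 96.43, 95.68, 94.96, in steps of 0.7 to 0.9.

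**Other interval method.** With a log-log Kaplan-Meier interval and no censoring, the lower limits for k = 1 to 4 are 93.11, 92.24, 90.99 and 89.69, in steps of 0.87, 1.25 and 1.30. This interval is not defined at k = 0. The message is the same.

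**If other-cause revisions are censored.** The plan does not say how the curve treats them. Suppose three are censored before one aseptic-loosening revision. The rate is 1 − 1/97 = 98.97%. Reattribute the first of the three: (1 − 1/100) × (1 − 1/97) = 97.98%. The move is 0.99 point, so censoring does not remove the effect.

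**How many events.** The documents state no expected count. Their one figure is in 1.1, where a review of 1851 obese patients' knees "using HVC mixed with Gentamicin showed one revision due to aseptic loosening". That is 1/1851 = 0.054%, or 0.05 expected events per 100, in a different population. At assumed true rates of 0.5%, 1%, 2% and 3%, the expected count per 100 is 0.5, 1, 2 and 3, and the chance of 0 to 3 events is 99.8%, 98.2%, 85.9% and 64.7%.

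**Why all-cause is the right bound.** All-cause failures include every aseptic-loosening failure, however it was labelled. If every revision is found and dated, the all-cause-free rate cannot exceed the true cause-specific rate.

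**The case against.** The strongest reply is that the attribution is not unchecked and the bound is nearly there.

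- **Checks on the entry.** The cause appears in three fields, the forms carry an investigator signature block, and the monitor compares them with source (8.3, 10.1). Events related or possibly related to the cement go to the sponsor for possible investigation (6.3, 6.4). This stands against any claim that one unchecked tick decides the result. But all three fields are site entries, monitoring tests agreement with the chart, and neither route is said to reclassify the endpoint.
- **Planned analyses.** Sections 9.2.1 and 9.4.1 show that all-cause revision was in view, so it would be wrong to say that nothing bounds the result. The gap is that neither item is designated for this purpose or clearly planned for both cements.
- **No decision rule.** This stands in full. A one-point shift reverses no formal conclusion.

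Three stronger readings are tempting, and the documents do not support them. A reader might infer that sites under-report loosening in the device's favour; this is a risk, and nothing shows that it happens. A reader might take the remark in 1.1, "Considering the exact cause may be unknown", as conceding that revisions cannot be classified; it concerns why debonding occurs, in failures already called aseptic loosening. A reader might also want the films reader in 7.1 to adjudicate every revision. The review "by an independent reviewer" covers radiolucency only, the forms do not collect operative and microbiology reports, and no film is required before an early revision. That would be a new task on new documents.

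**Conclusion.** The point holds as a gap in reporting. The primary rate depends on the site's attribution of cause, and the plan does not show by how much. The size is 1.0 point in the rate and 1.4 to 1.8 points in the exact lower limit for each reattributed revision per 100 knees, for assumed counts of 0 to 4 failures. This rests on 100 evaluable knees per cement and an exact two-sided interval, since the plan names no method.

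It is an inexpensive improvement to how the result is presented. It does not show that the primary rate is biased, and it does not mean that a formal decision would change.

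One matter comes first. Exclusion A in 5.1, read literally, removes every patient who has had revision surgery. If that covered revisions after the index operation, there would be no primary events to attribute and no all-cause bound to compute.

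**What to change.** 1. In 9.1.1 and 9.4.1, pre-specify for each cement the 24-month rate free of any revision or removal, with a 95% interval, and show it beside the primary rate as the conservative bound.
2. Optionally, add an intermediate analysis that counts as a failure every revision with no other specific cause documented in the chart. It relies on the treating site's own records, so it supplements the all-cause bound and does not replace it.
3. Correct 9.4.1 so that each cement has both an aseptic-loosening curve and an all-cause curve.
4. Give the Adverse Event form a date and a cause for every revision or removal.
5. State in 5.1 that exclusion A does not remove knees revised after the index surgery.

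The cost is slightly more chart abstraction, two more fields and a few more output lines. No new staff or independent adjudication is needed. The drawback for the sponsor is a second figure that may be less favourable than the first.
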